7.0 Data Collection & Storage

Aim 1 Data Collection:

Data will be collected to assess feasibility of screening, recruitment, randomization, and retention. We will also assess intervention engagement, treatment fidelity, and administration and completion of the outcome measures. These are described in greater detail below.

Intervention engagement: We will measure three indicators of participants' engagement with the intervention: (1) attendance at RECLAIM sessions; (2) attendance at optional check-in sessions; and (3) amount of independent/at-home practice. To assess independent/at-home practice, all participants randomized to the RECLAIM intervention arm will be provided an electronic mindfulness practice log sheet at the start of the study to track their engagement. Specifically, between RECLAIM sessions, participants will be asked to record how many days in the past week and approximately how many minutes per day they practiced mindfulness. They will also be asked to document any successes or difficulties that occurred. Practice log sheets will also ask participants to indicate how often they access the VA-approved cloud-based file storage application (e.g., Box) to use intervention materials (e.g., scripts, recordings). [Note: The VA-approved cloud-based file storage application will allow participants to access and download materials. The application will not allow participants to revise materials, upload their own materials, or provide any personal information (i.e., this application will not be used for data collection).] The practice log sheet can be completed electronically, or participants can print their log sheets to be completed manually. Participants can submit their practice logs to a member of the study staff via email. Additionally, at the beginning of each RECLAIM session, we will provide an electronic survey within the teleconferencing software that will match the questions/prompts on the participants' practice logs. This will provide participants another opportunity to submit their mindfulness practice information if they have not done so by email.

Practice feedback: At the start of each weekly session, we will engage in a discussion about participants' independent practice (e.g., successes and challenges) and engage in discussion on strategies to maximize facilitators and overcome barriers. We will do weekly reminder calls to make sure participants are completing their logs and this will be another opportunity to provide any additional information or feedback to assist participants' independent mindfulness practice.

Treatment fidelity: Intervention fidelity has been defined as the degree to which an intervention was delivered as conceived and planned.⁴⁶⁻⁵⁰ Fidelity of the RECLAIM intervention will be evaluated by the Principal Investigator (PI), [name], who will be co-facilitating the RECLAIM sessions, and the Project Manager, who will observe the eight RECLAIM sessions across all four cohorts. Fidelity will be assessed using a checklist, which will be iteratively refined throughout the Aim 1 pilot. The checklist will capture intervention content elements (e.g., presentation of reintegration challenges,

mindfulness practices), as well as unplanned components (e.g., discussion questions and participant responses). The fidelity checklist for RECLAIM will facilitate the larger prepare for the planned Hybrid Type I trial,¹¹¹ which will assess the effectiveness of RECLAIM while simultaneously planning for implementation.

Administration of outcome measures: Part of our feasibility assessment will be to determine the acceptability of measures administered, time for outcome measure completion, number of items missing, and follow-up rates. We will administer assessments after a Veteran has consented to study participation to measure (1) depression, (2) general difficulty adjusting to civilian life, (3) anxiety, (4) quality of life, (5) mindfulness, and (6) pain. Participants will complete outcome assessments at two timepoints: baseline and 2-month follow-up. Participants will receive a \$25 gift card for each outcome assessment they complete, for a possible total of \$50.

1. **Depression severity:** The Patient Health Questionnaire (PHQ-9) is a reliable and valid 9-item measure of depression severity used to screen, diagnose, monitor, and measure the severity of depression.³⁶ It is one of the most widely used, reliable, and validated measures of depressive symptoms.³⁶
2. **General difficulty adjusting to civilian life:** The Military to Civilian Questionnaire (M2C-Q) is an empirically validated self-report scale that measures general difficulty in readjusting to civilian life by assessing important indicators of reintegration challenges over the past 30 days including social/health behaviors, specifically interpersonal relationships; productivity at school, work, or home; community participation; self-care; leisure; and perceived meaning in life.³⁷ Research supports the construct and factor validity of scale scores and indicates high internal consistency (Cronbach's alpha = .92).³⁷
3. **Anxiety:** The Generalized Anxiety Disorder Scale (GAD-7) is a brief 7-item measure for assessing generalized anxiety disorder.⁵¹ The GAD-7 uses some of the Diagnostic and Statistical Manual of Mental Disorders (DSM-V) diagnostic criteria to assess generalized anxiety disorder. Scores classify respondents as having minimal, mild, moderate, or severe anxiety. The GAD-7 has good reliability and validity.⁵¹
4. **Quality of life:** The Veterans RAND Health Survey (VR-12) is a brief, self-administered health survey primarily used to measure health related quality of life.⁵²⁻⁵⁴ The VR-12 is one of the most widely used functional status measures and has been shown to be highly reliable and valid.⁵²
5. **Mindfulness:** The Five Facet Mindfulness Questionnaire (FFMQ) is a 15-item scale to measure five factors of mindfulness: (1) Observing; (2) Describing; (3) Acting with awareness; (4) Non-judging of inner experience; and (5) Non-reactivity to inner experience.⁵⁵ The FFMQ has strong psychometric properties, including good reliability for all facets (i.e., aspects) of mindfulness.^{37,56,57}
6. **Pain:** The PEG (pain intensity, interference with enjoyment of life, interference with general activity) is an ultra-brief measure that contains 3 items to assess pain levels on average, pain interference with enjoyment of life, and pain interference with general activity.⁵⁸ The PEG demonstrates strong reliability and validity.

Aim 2 Data Collection:

Interviews will take place using VA-approved teleconferencing software or over the phone. The Project Manager will conduct the interviews with pilot study participants. **Purpose:** Interviews will explore participants' experiences in the RECLAIM intervention. Interviews will also explore participants' perceived strengths of the intervention, suggestions for future improvements, and barriers and facilitators that impacted participation in RECLAIM. Interviews will take approximately 60 minutes to complete. Participants who engage in an interview will receive a \$50 gift card.

Aim 3 Data Collection:

No new data collection will occur in Aim 3. We will use data from Aims 1 & 2 to inform RECLAIM revisions.

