Intervention arm: Veterans randomized to the intervention arm (n=24) will participate in the 8-week RECLAIM intervention after 12 Veterans (i.e., a cohort) have been randomized. **Delivery of RECLAIM:** The RECLAIM intervention is comprised of (1) four 60-minute sessions that are delivered bi-weekly in a virtual group setting and (2) four bi-weekly coaching calls. Participants will also be offered an introductory session (i.e., Session 0) that will serve as a technical assistance session to ensure that participants can access Microsoft Teams and to try and mitigate connection challenges prior to the start of the intervention. The bi-weekly coaching calls will happen in the weeks between the virtual intervention sessions. Delivery of the bi-weekly intervention virtual sessions will be led by [name], who is a study consultant and an expert in mindfulness (e.g., certified as a Mindfulness Based Meditation for Pain Relief practitioner) and co-facilitated by [name]. Each RECLAIM session is structured with the following components to achieve this purpose: (1) an overview and discussion of the weekly topic, which is a domain of community reintegration; (2) a brief mindfulness practice (approximately 10 minutes); (3) reflection and discussion of the topic and mindfulness practice; (4) journal prompt and brief discussion; and (5) a discussion of ways to effectively engage in independent mindfulness practice(s). RECLAIM participants will be invited, but not required, to participate in optional check-in sessions which will occur between the regularly scheduled weekly RECLAIM sessions. The bi-weekly coaching calls will be conducted by the project manager ([name]) or [name].

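### The back-up practice survey asks about one week at sessions held every two weeks, so the weeks of home practice captured depend on how a Veteran reports

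*Combined protocol and SAP*

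**What the plan says.** Section 7.0 (Intervention engagement) names three engagement indicators: attendance at sessions, attendance at optional check-ins, and amount of independent practice. Practice is self-reported on a log held from the start of the study, on which "participants will be asked to record how many days in the past week and approximately how many minutes per day they practiced mindfulness".

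The information reaches the team by two routes:

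- **E-mail.** "Participants can submit their practice logs to a member of the study staff via email". No due dates are given.
- **Session survey.** "at the beginning of each RECLAIM session, we will provide an electronic survey within the teleconferencing software that will match the questions/prompts" on the logs. It is offered as "another opportunity to submit their mindfulness practice information if they have not done so by email".

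Section 6.0 (Intervention arm) describes an 8-week programme of "four 60-minute sessions that are delivered bi-weekly in a virtual group setting", with the coaching calls placed in the weeks between sessions. That placement gives bi-weekly the meaning of alternate weeks. Elsewhere the wording differs: section 6.0 also calls the sessions weekly when it describes the optional check-ins, and section 7.0 refers both to a weekly session (Practice feedback) and to eight sessions (Treatment fidelity).

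Section 7.0 (Practice feedback) adds: "We will do weekly reminder calls to make sure participants are completing their logs".

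The plan does not say how many log entries are due, whether one is due after the last session, or how entries from the two routes are combined. Section 8.0 says only that the feasibility assessments will use counts and percentages, with descriptive summaries.

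**The concern.** A 7-day question asked every 14 days leaves half of each interval unasked. If session 1 opens the programme, the survey given at its start asks about a week before any RECLAIM content was delivered. No survey follows session 4.

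The survey exists for Veterans who have not e-mailed their logs, so the gap falls on them. Two Veterans with identical practice can have different numbers of weeks on record because they reported differently. Any figure that sums practice over the programme then mixes behaviour with reporting route. Weeks that were never asked about cannot be recovered at analysis, so the remedy belongs in data collection.

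**Working it through.** The documents give no coverage figure to reproduce, so this is a count of days.

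**Inputs**

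- Programme length: 8 weeks = 56 days, numbered from day 0 (section 6.0).
- Survey window: the 7 days before each session (section 7.0).
- Sessions: four, 14 days apart (section 6.0, delivery description).
- Day of session 1: not stated. Assumed to be *s*, varied from 0 to 14.

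**Formula.** Sessions fall on days *s*, *s*+14, *s*+28 and *s*+42. The windows do not overlap. The last three lie wholly inside the programme and give 3 × 7 = 21 days. The window before session 1 adds min(*s*, 7) days. So:

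- days asked about = 21 + min(*s*, 7)
- days after the last session = 56 − (*s* + 42) = 14 − *s*

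| Reporting and schedule | Days asked about | Share of 56 days | Missed | Days after last session |
|---|---|---|---|---|
| Survey only, four sessions, *s* = 0 | 21 + 0 = 21 | 37.5% | 62.5% | 14 |
| Survey only, four sessions, *s* = 7 | 21 + 7 = 28 | 50% | 50% | 7 |
| Survey only, four sessions, *s* = 14 | 21 + 7 = 28 | 50% | 50% | 0 |
| Survey only, eight weekly sessions from day 0 | 7 × 7 = 49 | 87.5% | 12.5% | 7 |
| Weekly e-mailed logs | up to 56 | up to 100% | 0% if all returned | covered if a final log is sent |

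Between session 1 and session 4 there are 3 × 14 = 42 days, of which the surveys cover 3 × 7 = 21. That is 50% whatever the value of *s*.

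**Effect on a practice figure.** For illustration, assume a Veteran practises 5 days × 10 minutes = 50 minutes every week.

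- True total: 8 × 50 = 400 minutes. Eight weekly logs record 400.
- Survey only, *s* = 0: 3 × 50 = 150 minutes, which is 62.5% below 400 if unasked weeks are treated as zero.
- Survey only, *s* = 7 or 14: 4 × 50 = 200 minutes, 50% below on the same treatment.
- Mean per reported programme week: 150 / 3 = 50 and 400 / 8 = 50, so there is no difference.
- If *s* = 0 and the session-1 answer is pooled as a programme week, with pre-programme practice assumed to be zero: (0 + 150) / 4 = 37.5 minutes, 25% below 50.

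Totals are therefore sensitive to route. A per-week mean is robust in this constant-practice example, provided that the session-1 answer is kept apart. It would still rest only on the week before each session, so it could be off in either direction if practice differs between the two weeks of an interval.

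**The case against.** The strongest reply is that the survey is only a supplement. Logs are available throughout, can be e-mailed at any time, and are prompted by weekly calls. A past-week question suits a log completed weekly. This stands: a reader might infer that the practice log itself is faulty, and the documents do not support that. It does not close the gap for Veterans who rely on the survey. The reminder calls prompt completion, but the plan does not say that practice data are recorded on them, nor that an entry is due every week.

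Second, the two-week spacing is not settled, because other sentences describe weekly or eight sessions. This also stands. On that reading, with session 1 on day 0, the survey misses 12.5%, so the loss of at least half is conditional on the delivery description in section 6.0.

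Third, a reader might infer that survey users lose 62.5% of their practice and will look less engaged by that amount. The documents do not support this. The figure is the top of a 50% to 62.5% range, it compares a Veteran who e-mails every log with one who e-mails none, and it requires unasked weeks to be counted as zero, which the plan nowhere states. Use of both routes would shrink the gap.

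Finally, the plan sets no progression threshold on practice and plans no dose estimate from it, so no decision rule is shown to be distorted.

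**Conclusion.** The point holds in a limited form. Under four sessions two weeks apart, the back-up survey covers one of the two weeks since the previous session. A Veteran reporting only by survey is asked about 37.5% to 50% of the 8 weeks. The range rests on an assumed day 0 to 14 for session 1. If session 1 opens the programme, its survey describes pre-programme practice. No survey covers time after session 4, which is 0 to 14 days within the 8 weeks over the same range.

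The number of weeks captured, and any total, depends on reporting route; a weekly average is much less affected. The statements on session frequency and number in sections 6.0 and 7.0 contradict one another and must be reconciled.

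The impact is modest: practice is one of three engagement indicators, summarised descriptively, in an intervention arm of 24. The change is worth making because it is cheap and the missing weeks cannot be recovered later.

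**What to change.** 1. Reconcile the statements on session frequency and number in sections 6.0 and 7.0.
2. In the session survey, ask days and minutes separately for each week since the previous session. This wording works under either schedule.
3. State that one log entry is due per week.
4. Collect the weeks after the last session at the final coaching call or the 2-month assessment.
5. If session 1 opens the programme, flag its answers as pre-programme practice and keep them out of programme averages.
6. In section 8.0, report practice per reported week, with the number of weeks reported and the route, and do not count unreported weeks as zero.

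The cost is one extra row in the survey, one closing entry at a contact already planned, and a few sentences of text. The small downside is that recall of the earlier week will be slightly less accurate.

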- The PI will determine if an event is an adverse event (AE) or a serious adverse event (SAE) by assessing if it is 1) unexpected, 2) related or possibility related to study participation, AND 3) suggests that the research places subjects or others at a greater risk of harm than was previously known. Serious adverse events must be determined by the PI as both unanticipated and related to the research study.
- Upon becoming aware of a serious adverse event, which was both unanticipated and related to the research, the study team will immediately (within 24 hours) notify the IRB via verbal notification. A written notice to the IRB will be submitted within 5 business days following the event.
- Data collection on AEs and SAEs will begin at the time participants have been provided the Study Information Sheet and will be kept on a tracking log by the program manager.

Additionally, this study will adhere to VA and university regulations in conducting studies with human subjects. Adverse psychosocial reactions by participants and risks to confidentiality and data security (detailed in section 12.0 below) will be minimized through: informing potential participants in advance of the nature of the project, the nature of the questions to be asked, and the individual's right to decline to answer any or all questions; providing full and proper training to research staff; never sharing research findings about one participant with another participant; keeping paper documents in locked cabinets in locked offices; and ensuring that compensation is non-coercive.

If there is a suspected or confirmed loss of information, the PI will ensure that the event is reported to the IRB according to IRB policy and to the VA Privacy Officer.

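### Section 9.0 defines AEs and SAEs by an unanticipated-problem test with no seriousness criterion, so its text does not require logging of serious events judged unrelated or expected

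*Combined protocol and SAP*

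**What the plan says.** Section 9.0 opens by stating that no adverse events are anticipated and that local IRB guidelines on reporting them will apply. Its bullets then set the study's own rules.

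- **Classification.** The first bullet says "The PI will determine if an event is an adverse event (AE) or a serious adverse event (SAE") and gives three conditions joined by AND. The event must be unexpected, it must be "related or possibility related to study participation", and it must be one that "suggests that the research places subjects or others at a greater risk of harm than was previously known". The bullet ends: "Serious adverse events must be determined by the PI as both unanticipated and related to the research study".
- **IRB notice.** The 24-hour verbal notice applies "Upon becoming aware of a serious adverse event, which was both unanticipated and related to the research".
- **Log.** Data on AEs and SAEs are collected from the point at which the Study Information Sheet is provided, and "will be kept on a tracking log by the program manager".

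A later paragraph of section 9.0 commits the study to VA and university regulations in general terms. Section 7.0 (Treatment fidelity) says that the PI co-facilitates the RECLAIM sessions. Section 4.0 (Mental health screening) sets out a separate response to suicidal ideation and repeats the screening measures at each outcome assessment. Section 8.0 does not mention adverse events.

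**The concern.** Three separate questions are folded into one test: what counts as an untoward event, whether it is serious, and whether it needs prompt reporting to the IRB. The conditions used are those of an unanticipated problem, which the section heading names alongside adverse events. They suit the third question. Used for the first, they make causal attribution the condition for entry to the log, when it should be a field in the log.

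The pilot enrols Veterans with depressive symptoms and is meant to prepare a larger randomised trial. If section 9.0 is followed as written, the harms log passed to that trial has already been filtered by the judgement of someone who helps to deliver the intervention. Serious events cannot then be tabulated by arm from the log independently of that judgement.

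**Working it through.** The documents state no figure to reproduce. The check applies the rule in section 9.0 to a serious event.

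**Inputs.** The three-part test, the extra SAE condition, the scope of the log and the notice trigger all come from section 9.0. The extra SAE condition is read as necessary, not as a second complete definition. Arm sizes come from section 2.0 (48 in total) and section 6.0 (24 in the intervention arm), so 48 − 24 = 24 controls.

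| PI's judgement of a serious event | Three-part test | Extra SAE condition | Logging required by section 9.0 | 24-hour notice |
|---|---|---|---|---|
| Unrelated | fails | fails | no | no |
| Expected | fails | fails | no | no |
| Unexpected, possibly related, greater risk | passes | fails | yes, as an AE | no |
| Unexpected, related, greater risk | passes | met | yes, as an SAE | yes |
| Unexpected, possibly related or related, no greater risk | fails | met only if related | no | no |

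**Step 1: unrelated or expected events.** With two levels of expectedness, three of relatedness (unrelated, possibly related, related) and two of greater risk, there are 2 × 2 = 4 unrelated combinations and 3 × 2 = 6 expected ones. Two combinations are both. None of them passes. These are counts of logical cases and say nothing about how often events occur.

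**Step 2: seriousness.** It is not an input to any column, so the table would be the same for a trivial event. A minor event in the fourth row meets every stated condition for an SAE. A death in the first row meets none.

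**Step 3: possibly related events.** The first bullet accepts possible relatedness for the joint AE/SAE test, but its last sentence and the notice bullet require relatedness. A possibly related serious event is therefore logged, as an AE at most, and falls outside the 24-hour notice.

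**Step 4: comparison by arm.** For an arm of size n with event rate r and probability p that an event passes the test, the expected number logged is n × r × p. With n = 24 in each arm, the ratio of expected logged counts is (r₁/r₂) × (p₁/p₂). It equals the ratio of event rates only if p₁ = p₂. The documents give neither r nor p. There is reason to doubt equality: control participants receive only a reading list, with fewer contacts by design (section 6.0), so the PI may find relatedness less readily there. That is an inference, not a figure from the plan.

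**Step 5: data outside the filter.** The PHQ-9 is scheduled at baseline and at 2 months in both arms. After randomisation that gives at most 48 × 1 = 48 readings, 24 per arm, whatever the PI's attribution.

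**The case against.** The strongest reply is that section 9.0 is not the whole rule. It defers to local IRB guidelines and to VA and university regulations, which may require wider recording. This stands as a limit on the conclusion: the gap is in the protocol text and is not shown to be a gap in practice. It does not remove the point, because those sources are not reproduced and the IRB sentence concerns reporting, not what goes on the log.

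A second reply is that the notice bullet adds a qualifier that would be redundant if every SAE already met it, so a wider class of SAE may be intended. That is plausible, but no wider class is defined, and the first bullet makes the same features part of being an SAE.

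A reader might infer more than the documents support:

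- *That the two sentences of the first bullet contradict each other.* Read as nested conditions they do not. A possibly related event is an AE that misses the SAE condition.
- *That unlogged harms could never be looked at again.* PHQ-9 data, with the C-SSRS where triggered, are collected regardless of attribution, and the study has VA medical record access. No retrospective review is planned, but the loss is not total.
- *That suicidal participants are left without a response.* The section 4.0 pathway does not depend on AE classification. Veterans with severe scores or an endorsed item 9 are kept in only after consultation on whether continuing is appropriate.
- *That attribution by the PI is improper in itself.* Nothing in the documents says so. The difficulty is that attribution comes before logging.
- *That section 9.0 contradicts section 11.0 on what is anticipated.* Planning to minimise "Adverse psychosocial reactions by participants and risks to confidentiality and data security" is mitigation and need not mean that such reactions are anticipated. If no adverse event is anticipated, most events are unexpected on their face, and relatedness and greater risk do most of the filtering.

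**Conclusion.** The point holds for the text of section 9.0. One unanticipated-problem test defines both AEs and SAEs, no seriousness criterion separates them, and the log takes its scope from that test. A serious event that the PI judges unrelated or expected is not required to be logged, and a possibly related one is at most an AE without the 24-hour notice.

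The number of events affected cannot be estimated, because the documents give no event rate and no rate of attribution. The effect is on which events the log must contain, in a trial of 48 participants. The conclusion assumes that the SAE sentence is a necessary condition and that no outside rule, unseen here, widens the log. It should be fixed: this is a stated rule that yields a selective harms record, not just missing detail, and the change is small.

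**What to change.** - In section 9.0, log every untoward event in both arms whatever its attribution. Record seriousness (defined by outcome), expectedness and relatedness as separate fields.
- Keep the three-part test only as the filter for prompt IRB reporting, and check the result against the IRB, VA and university rules that the section cites.
- Reconcile related with possibly related across the classification and notice bullets. While editing, state whether the written notice runs from awareness, as the verbal one does, or from the event ("A written notice to the IRB will be submitted within 5 business days following the event"). This second item is minor.
- In section 8.0, add one sentence saying that logged events will be summarised descriptively by arm.

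Asking both arms the same adverse-event question at 2 months would make capture more comparable, but it is optional and goes beyond repairing the definition.

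The cost is an amendment to section 9.0, one sentence in section 8.0, extra fields on the existing log, slightly more logging and higher reported event counts. No clinical procedure changes.
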